## **1. Background and Rationale**

Total hip arthroplasty (THA) is widely performed for traumatic hip fractures and degenerative hip disease in older adults and is associated with substantial postoperative pain that can delay mobilization and prolong hospital stay. Effective multimodal analgesia is essential to facilitate early rehabilitation and reduce opioid-related adverse effects in this vulnerable population.

Opioid analgesics provide rapid pain relief but carry important risks in elderly patients, including respiratory depression, delirium, constipation, nausea/vomiting, and prolonged hospitalization. Regional anesthesia techniques, particularly peripheral nerve and fascial plane blocks, are increasingly used as opioid-sparing strategies after THA.

The pericapsular nerve group (PENG) block targets the articular branches of the femoral, obturator, and accessory obturator nerves supplying the anterior hip capsule via local anesthetic injection between the psoas tendon and superior pubic ramus. It has been described as providing effective, largely motor-sparing postoperative analgesia for hip surgery and acute pain after hip fracture.

The anterior quadratus lumborum block (AQLB) deposits local anesthetic in the fascial plane between the quadratus lumborum and psoas major muscles, aiming to block lumbar plexus articular branches and provide analgesia for hip surgery. Previous studies reported favorable analgesic profiles of AQLB in THA.

Both PENG and AQLB appear anatomically capable of covering the operative field in THA, but they may differ in their balance between analgesic efficacy, opioid-sparing effect, and motor impairment. Comparative data between these two techniques in elderly

patients undergoing THA under general anesthesia are limited. This trial evaluates whether ultrasound-guided PENG block or AQLB offers superior postoperative analgesia and functional recovery compared with standard opioid-based analgesia and compares PENG and AQLB directly.

## **2. Study Objectives**

### **2.1 Primary Objective**

To compare total intravenous morphine consumption in the first 24 hours after surgery among three groups of elderly patients undergoing unilateral THA under general anesthesia: PENG block group, AQLB group, and Control group (opioid analgesia only).

### **2.2 Secondary Objectives**

To compare intraoperative fentanyl consumption between the three groups.

To compare time to first rescue analgesia postoperatively.

To compare Numeric Pain Rating Scale (NRS) scores at rest and during passive 90° hip flexion at predefined postoperative time points (30 min, 2, 4, 6, 8, 12, 18, and 24 hours).

To assess block failure rate, defined as the requirement for more than one rescue morphine dose in the first postoperative hour.

To compare motor recovery (manual muscle test for quadriceps and iliopsoas, and active hip flexion range of motion) over the first 24 hours.

To compare time to first ambulation and length of hospital stay.

To compare intraoperative hemodynamic profiles (heart rate and mean arterial pressure).

To compare the incidence of block-related complications and morphine-related adverse events (e.g., nausea/vomiting, respiratory depression, hypotension, falls).

To compare block performance time and surgical duration between groups.

### **3. Study Design**

This is a prospective, randomized, double-blind, parallel-group clinical trial with three arms (PENG, AQLB, and Control) with equal allocation (1:1:1). The study is conducted at a single tertiary university hospital (Orthopedic Surgical Theater, Cairo University Hospital). Patients and outcome assessors are blinded to group assignment; the anesthesiologist performing the block is not involved in postoperative assessments.

### **4. Study Population**

#### **4.1 Inclusion Criteria**

Age  $\geq$ 65 years.

Male or female patients with traumatic hip fracture scheduled for elective unilateral THA via an anterolateral approach.

Planned anesthesia: general anesthesia.

Body mass index (BMI) 20–35 kg/m^2.

American Society of Anesthesiologists (ASA) physical status I–III.

Provision of written informed consent.

#### **4.2 Exclusion Criteria**

Known allergy or contraindication to local anesthetics (bupivacaine) or opioids.

History of psychological disorders and/or chronic pain requiring long-term analgesic therapy.

Pre-existing peripheral neuropathy affecting lower limbs.

Coagulopathy or current anticoagulant therapy precluding regional blocks.

Unstable or severe cardiac disease (e.g., unstable coronary syndromes).

Acute respiratory disease (e.g., active chest infection, respiratory failure).

Advanced liver disease (liver enzymes  $>3\times$  upper limit of normal).

Severe renal impairment (serum creatinine  $>2$  mg/dL).

Local infection at the intended needle puncture site.

Expected operative duration  $>3$  hours.

Refusal to participate.

#### **4.3 Withdrawal Criteria**

Withdrawal of consent at any time.

Intraoperative events requiring deviation from protocol (e.g., conversion to different surgical procedure).

Significant protocol violations deemed to invalidate study data (to be documented and evaluated case by case).

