## **7. Outcomes and Assessments**

### **7.1 Primary Outcome**

The primary outcome is total morphine consumption (mg) in the first 24 postoperative hours, calculated as the cumulative dose of intravenous morphine administered in the PACU and on the ward up to 24 hours after surgery.

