## **11. Statistical Analysis Plan**

### **11.1 General Principles**

Statistical analyses will be performed using IBM SPSS Statistics (version 28). All randomized participants who receive the allocated intervention and have outcome data will be included in the primary analysis (modified intention-to-treat). Two-sided tests will be used with a significance level of  $P < 0.05$ . Continuous variables will be assessed for normality using the Shapiro–Wilk test and visual inspection of histograms and Q–Q plots. Normally distributed variables will be presented as mean  $\pm$  standard deviation and non-normally distributed variables as median (interquartile range). Categorical variables will be presented as counts and percentages. Adjustment for multiple pairwise comparisons will use Bonferroni correction where applicable.

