### **11.2 Analysis Populations**

The Full Analysis Set (FAS) includes all randomized participants who receive the allocated intervention and provide at least one primary outcome measurement. The Per-

Protocol Set (PPS) includes participants without major protocol deviations that could influence the primary outcome. The primary analysis will be performed on the FAS; sensitivity analyses may be repeated on the PPS if protocol deviations occur.

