### **11.3 Handling of Missing Data**

The study is expected to have minimal missing data due to the short follow-up period. If missing data occur, the primary approach will be complete-case analysis. Reasons for missingness will be documented. No formal imputation strategy is planned.

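### Section 4.3 allows randomised patients to be withdrawn for deviations that section 11.2 would keep in the primary set; the two are not reconciled, and follow-up of withdrawn patients is not stated

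*Combined protocol and SAP*

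**What the plan says.** Section 4.3 gives three grounds for withdrawal. Besides withdrawn consent, they are "Intraoperative events requiring deviation from protocol (e.g., conversion to different surgical procedure") and "Significant protocol violations deemed to invalidate study data (to be documented and evaluated case by case"). The case-by-case wording belongs to the violations only.

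Section 11.2 defines the FAS as "all randomized participants who receive the allocated intervention and provide at least one primary outcome measurement". Section 11.1 describes the primary analysis in similar terms. Neither excludes anyone for a deviation; that is left to the PPS. On the roles of the two sets, section 11.2 says: "The primary analysis will be performed on the FAS; sensitivity analyses may be repeated on the PPS if protocol deviations occur".

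Section 11.3 adds: "If missing data occur, the primary approach will be complete-case analysis". It plans no imputation, but does require reasons for missing data to be documented.

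Under section 9 the envelope is opened after induction. Patients, surgeons, ward staff and outcome assessors are blinded. The anesthesiologist who gives the block knows the arm but takes no part in postoperative assessment.

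**The concern.** The block is a single injection before surgery (sections 6.2.1 and 6.2.2), so withdrawal afterwards cannot stop any further block treatment. The third ground in 4.3 is about whether the data are usable, not about consent or safety, so it can easily be read as a rule for excluding data. Both disputed grounds act after randomisation.

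Read that way, 4.3 removes from the primary analysis the patients whom 11.2 would keep. The exclusion could be informed by the allocation. For violations that happen after surgery, it could also be informed by morphine use, which is the primary outcome. The trial would then lose the protection of randomisation in a way that its own sensitivity analyses could not detect.

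**Working it through.** **Step 1. Follow one patient through the plan.** Take a patient who received the allocated block and then had a major deviation.

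- Under 11.2 alone, the patient has a morphine total, is in the FAS and is left out of the PPS. A comparison of FAS and PPS shows the effect of the deviation.
- If 4.3 is applied first and data collection stops, there is no complete 24-hour total. The outcome is the "cumulative dose of intravenous morphine administered in the PACU and on the ward up to 24 hours after surgery", and the plan does not say whether a part-day sum counts. Complete-case analysis drops the patient from the FAS as well. FAS and PPS move towards the same set, and their agreement says nothing about the loss.
- The optional analyses in 11.7 exclude deviations or extreme morphine values. They remove more patients and restore none.

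**Step 2. What could inform the decision.** A withdrawal made during surgery comes before any postoperative morphine. It can be allocation-informed, because one person in theatre knows the arm, but not outcome-informed. A postoperative violation can be tied to the outcome: off-protocol analgesia, or morphine above the 24-hour cap stated in 6.4, which by construction marks the highest totals. The blinded roles in section 9 do not include the principal investigator or the analyst, and section 12 sets up no independent monitoring committee.

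**Step 3. The plan's own allowance.** Section 8 gives 81 evaluable patients, about 15% attrition and a target of 93. With one-way ANOVA, three groups, α = 0.05, and the stated 0.35 read as Cohen's f (the type is not stated), the noncentral F distribution gives 79.6% power at N = 81, close to the stated 80%. Then 81 × 1.15 = 93.15, which matches 93. The gap is 93 − 81 = 12 patients (12/93 = 12.9%). Power is 85.3% at 93, 79.6% at 81 and 76.1% at 75, so the power cost of losing patients is modest. Selective loss matters more.

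**Step 4. Illustration of selective loss.** Assumptions, none of them from the documents: no true difference, 31 per arm, the m highest values removed from each block arm, none removed from Control. The entries are rejection rates of the planned Kruskal–Wallis test at 0.05.

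| m per block arm | Normal | Lognormal | Capped Poisson, mean 3 | Capped Poisson, mean 4 |
|---|---|---|---|---|
| 0 | 4.6% | 4.8% | 5.4% | 4.9% |
| 1 | 6.1% | 5.7% | 5.9% | 6.0% |
| 2 | 8.5% | 7.8% | 9.5% | 8.1% |
| 3 | 11.4% | 11.5% | 12.1% | 11.8% |

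The normal and lognormal columns use 10,000 runs. The Poisson columns count boluses, capped at 6, with an assumed weight of 75 kg (SD 12), and use 4,000 runs. Near 8.5%, the simulation standard error is √(0.085 × 0.915/10,000) = 0.28 percentage points, or 0.44 with 4,000 runs. Random removal of one to three patients per block arm gave 4.7% to 5.3% in the normal and lognormal settings.

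Three removals per block arm is 6 patients, half of the 12-patient gap in step 3. As a check on scale, dropping the top two of 31 normal values lowers the arm mean by (2.06 + 1.63)/29 = 0.127 SD.

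**The case against.** A reader might infer that the investigator withdraws patients knowing their arm and their morphine use. The documents do not support that. They name no decision-maker and do not say that decisions are unblinded or outcome-informed. Most roles are blinded, and the one described as unblinded is kept out of postoperative assessment. What stands is that the plan does not rule such decisions out.

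A reader might also infer that 4.3 orders data to be discarded. It does not. Withdrawal could mean leaving the remaining study procedures, such as pain scoring during passive hip flexion and motor testing. Medication records are source documents (section 10), so a withdrawn patient whose morphine is recorded could still meet the FAS definition. Data loss is therefore possible, not stated.

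Heavy use of rescue morphine within the cap is not a violation. It is the protocol's own rescue, and block failure is a named secondary outcome (section 7.2). Only use above the cap or off-protocol analgesia fits the concern. Either can occur in Control, where removal would bias against the blocks.

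The simulation is a constructed worst case. If each of two removals per block arm has only a 50% chance of being the top user, the error rate is about 6–7%. The attrition allowance is a sample-size margin, not a forecast of withdrawals.

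These points limit the claim. They do not reconcile 4.3 with 11.2, and they do not supply the missing statement on follow-up.

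**Conclusion.** The point holds as an unreconciled rule with missing safeguards. Section 4.3 permits discretionary removal of randomised, treated patients; 11.2 would keep them; 11.3 turns withdrawal without 24-hour data into exclusion; and neither the PPS nor the outlier analyses would reveal it.

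The direction of any bias depends on which arm loses patients. The documents give no expected number of 4.3 withdrawals, so the size is unknown. The roughly 6%, 8–9% and 11–12% in the table rest wholly on the assumed pattern of removals and are not an estimate for this trial. With unrelated removals there is essentially no inflation. This is a cheap improvement, not a fault that invalidates the design.

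**What to change.** In section 4.3, separate stopping protocol procedures from withdrawal from follow-up, and let only the patient's refusal of further data collection end data collection. State that patients with a changed procedure or a protocol violation who received the allocated intervention still have 24-hour morphine recorded from routine charts, with the other outcomes where feasible, and remain in the FAS.

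In section 11.2, have deviations classified as major or minor before database lock by an existing team member blinded to arm and to morphine totals, and use that list only to form the PPS.

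The cost is protocol and SAP wording. The charts are already source documents and the sample size does not change. The downside is slight extra variance from a few atypical patients.

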## **5. Ethical and Regulatory Considerations**

The study was approved by the Research Ethics Committee, Faculty of Medicine, Cairo University (ID: MD-16-2022, approval date 16 March 2022). The trial is registered at ClinicalTrials.gov (NCT06679764). All participants (or their legal representatives) receive detailed verbal and written information about the study and sign a written informed consent form prior to any study procedure. Data confidentiality is maintained according to institutional and national regulations. Participant identities are coded and not included in reports or publications.

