### **6.4 Postoperative Management**

In the post-anesthesia care unit (PACU), patients are monitored for 2 hours. NRS scores at rest and during movement, mean arterial pressure, and heart rate are recorded on arrival. On the ward, patients receive paracetamol 500 mg IV every 6 hours. Rescue analgesia consists of morphine 0.05 mg/kg IV bolus when NRS  $\geq 4$  at rest or during movement, with a maximum dose of 0.3 mg/kg in 24 hours. Ondansetron 0.1 mg/kg IV is administered for moderate or severe postoperative nausea/vomiting.

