### **7.2 Secondary Outcomes**

To compare intraoperative fentanyl consumption between the three groups.

To compare time to first rescue analgesia postoperatively.

To compare Numeric Pain Rating Scale (NRS) scores at rest and during passive 90° hip flexion at predefined postoperative time points (30 min, 2, 4, 6, 8, 12, 18, and 24 hours).

To assess block failure rate, defined as the requirement for more than one rescue morphine dose in the first postoperative hour.

To compare motor recovery (manual muscle test for quadriceps and iliopsoas, and active hip flexion range of motion) over the first 24 hours.

To compare time to first ambulation and length of hospital stay.

To compare intraoperative hemodynamic profiles (heart rate and mean arterial pressure).

To compare the incidence of block-related complications and morphine-related adverse events (e.g., nausea/vomiting, respiratory depression, hypotension, falls).

To compare block performance time and surgical duration between groups.

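### No eligibility criterion requires that the patient can use the NRS, the only stated trigger for the morphine that makes up the primary outcome

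*Combined protocol and SAP*

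**What the plan says.** **Consent.** Section 5 states that "All participants (or their legal representatives) receive detailed verbal and written information about the study and sign a written informed consent form", and places this before any study procedure. The matching inclusion item in 4.1 is "Provision of written informed consent"; it does not say who must sign.

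**Population.** Section 4.1 sets a minimum age of 65 and enrols "Male or female patients with traumatic hip fracture scheduled for elective unilateral THA via an anterolateral approach".

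**Cognition.** Sections 4.1 and 4.2 contain no cognitive screen, no dementia or delirium exclusion, and no requirement to be able to rate pain. The nearest item is in 4.2: "History of psychological disorders and/or chronic pain requiring long-term analgesic therapy". Psychological disorder is not defined there. The withdrawal criteria in 4.3 do not mention a patient who cannot report pain; the closest is the general item "Significant protocol violations deemed to invalidate study data (to be documented and evaluated case by case".

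**Outcome chain.** Section 6.4 says "Rescue analgesia consists of morphine 0.05 mg/kg IV bolus when NRS" is 4 or more, at rest or on movement. It gives no other way of establishing need. Section 7.1 defines the primary outcome from these doses, "calculated as the cumulative dose of intravenous morphine administered in the PACU and on the ward up to 24 hours after surgery". The same scale is a secondary outcome at eight time points in 7.2: "To compare Numeric Pain Rating Scale (NRS) scores at rest and during passive 90° hip flexion at predefined postoperative time points".

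**The concern.** A numeric pain rating is something the patient gives. The documents do not use the word self-report, but it follows from the choice of scale. If a patient cannot understand the scale, the number recorded, or the absence of one, says little about pain. The morphine that depends on it then says little about analgesic need.

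The rest of the plan does not catch this. A total of zero or near zero is a recorded value, not a missing one. The patient therefore meets the Full Analysis Set definition in 11.2, and the complete-case approach in 11.3 does not remove them. The outlier analysis in 11.7 is optional and gives no rule that would identify them.

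Several secondary outcomes inherit the problem. Block failure is counted from rescue doses in the first hour, and time to first rescue depends on the same trigger. The NRS scores are affected directly. The manual muscle test and active hip flexion also need a patient who can follow instructions.

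**Working it through.** **1. Trace one patient through the plan.** Take a patient who cannot rate pain and whose legal representative signs.
- Eligibility (4.1, 4.2): no item tests ability to use the NRS. The psychological-disorder item might or might not be applied.
- Withdrawal (4.3): no item applies by its terms.
- Rescue (6.4): depends on an NRS of 4 or more, with no stated alternative.
- Primary outcome (7.1): the sum of whatever was given.
- Analysis (11.2, 11.3): a total exists, so the patient is included.

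**2. Direction of the effect.** Under section 9 the envelope is opened only after induction, so consent and eligibility are settled before the arm is known. Such patients should be spread evenly over the three arms on average. Unreliable reporting affects Control totals as well as block totals.

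**3. Reproduce the plan's sample size.** Inputs from section 8: effect size 0.35, alpha 0.05, power 80%, three groups, 81 patients, 93 after attrition. Reading 0.35 as Cohen's f in a one-way ANOVA, the noncentrality parameter is λ = N·f², with 2 and N − 3 degrees of freedom.
- N = 81: λ = 81 × 0.35² = 9.92, power 79.6%.
- N = 93: λ = 93 × 0.35² = 11.39, power 85.3%.

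The smallest N that reaches 80% is 82, so the plan's 81 is reproduced to within one patient. Read as a two-group standardised difference, 0.35 would need 129 per arm, so f is the reading that fits.

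**4. Illustrate the dilution.** Assumption, not in the documents: a share q of each arm contributes no between-arm difference, and the SD is unchanged. Then f becomes 0.35 × (1 − q).

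| q | f | Power, N = 81 | Power, N = 93 |
|---|---|---|---|
| 0% | 0.350 | 79.6% | 85.3% |
| 5% | 0.3325 | 75.1% | 81.3% |
| 10% | 0.315 | 70.2% | 76.7% |
| 20% | 0.280 | 59.2% | 65.9% |

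**5. Compare with leaving these patients out.** If the same share is excluded and not replaced, f stays at 0.35 and N becomes 81 × (1 − q). Power is 77.3%, 74.8% and 69.1% for q = 5%, 10% and 20%. Each figure is higher than the corresponding N = 81 figure in step 4. If recruitment continues to the target, the planned power is kept.

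**The case against.** **Sections 4.1 and 5 do not conflict.** A reader might infer that 4.1 demands the patient's own signature and that section 5 contradicts it. It does not: 4.1 asks for written consent without naming the signatory, and a representative's written consent satisfies it. This objection stands in full.

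**The proxy wording does not show that patients without capacity are expected.** It is a bracketed phrase in a general ethics paragraph and may be standard text. It permits a route and no more. This also stands; the point rests on what the plan allows, not on a forecast of who will enrol.

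**The psychological-disorder exclusion may remove some of these patients.** It may, if a site reads it that way. Because it is undefined and tests nothing, it narrows the gap without closing it.

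**A low total from under-reporting could be taken to flatter a block.** A reader might infer bias in favour of PENG or AQLB. The documents do not support that, because allocation follows eligibility and the same under-reporting lowers Control totals. Only dilution and noise are supported.

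**The power figures rest on an assumed q.** They also hold the SD fixed, although totals near zero would change it, and they use ANOVA where 11.5 specifies Kruskal–Wallis for non-normal data. At the full 93 patients and q = 5%, power is still 81%. These limits stand, so the figures illustrate the mechanism and do not measure the defect.

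**Conclusion.** The gap is real and worth closing. The plan allows proxy consent, sets no requirement on ability to use the NRS, and builds its primary outcome from doses whose only stated trigger is that scale. Patients whose primary outcome is not a valid measure can enter and remain in the main analysis.

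The expected consequence is a smaller apparent difference between arms and more noise in the primary, NRS, time-to-rescue, block-failure and motor outcomes. On the stated assumptions, power at N = 81 drops by about 4 points (79.6 − 75.1) at q = 5% and about 20 points (79.6 − 59.2) at q = 20%. The true q is not in the documents and may be small. The absence of the criterion is certain; the size of its effect is not.

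**What to change.** Add one line to 4.2: *Inability to understand and use the 0–10 NRS after instruction, assessed before randomisation at the consent discussion.* The documents do not state the range of the scale; 0–10 is assumed here and should be confirmed. The consent discussion is the natural place for the check, because section 5 already requires it and the documents describe no separate preoperative visit.

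Add one sentence to section 5: *Consent by a legal representative does not waive this criterion.* Proxy consent need not be deleted. A blanket dementia exclusion is also unnecessary, since it would remove patients who can use the scale.

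The cost is two lines of text and a brief check. Slightly fewer patients will be eligible, and the results will not extend to patients who cannot report their own pain. The criterion does not cover delirium that arises after surgery, a risk that section 1 itself names; the trial would still carry that source of noise.
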